4. STUDY DESIGN

4.1. Overall Design

This study will test our hypothesis that HD-tDCS will improve performance on language tasks by increasing functional connectivity and by regulating abnormal neuronal oscillatory patterns. The language performance and functional connectivity changes will be determined in a randomized, double-blind, sham-controlled crossover manner, in which a stimulation of up to 2mA in the targeted cortical tissue or sham is administered to 20 IvPPA subjects age 45 years and older. The order of treatments is counterbalanced in a within-subject crossover design, as illustrated in Fig. 2 below. In brief, study participants will receive sham during one treatment period and stimulation during the other treatment period.

Figure 2. Study Design and tDCS Treatment Protocol

The Screening Visit includes medical history, Language Assessment battery, MRI safety screening, and TMS Neuronavigation. Visit 1 (Baseline) will include fMRI and MEG. Additionally at Visit 1, and for 9 additional days in a two-week period (Tx Period 1), each subject will undergo real stimulation or sham and simultaneous word and non-word reading and repetition tasks. At the end of Tx Period 1, a 16-week washout period begins. After the first 8 weeks of the 16-week washout period, subjects return for Assessment Visit 1 where they receive the Language Assessment battery, including the reading and non-word repetition tasks tested at baseline, and 'trained' during each of the stimulation sessions. After the 16-week washout period, Tx Period 2 begins. Subjects undergo stimulation or sham and the simultaneous word and non-word reading and non-word repetition tasks for 10 days over a two-week period. Eight weeks after the end of Tx Period 2, subjects receive the Language Assessment Battery at Assessment Visit 2, which is the last study visit.

An unblinded member of the study team having no contact with the study subjects will randomize them to the treatment conditions, while the language assessment battery of tests will be delivered by a blinded member of the study team. The language training exercises used during each tDCS session as well as the tDCS intervention itself will be delivered by a blinded, qualified and formally tDCS-trained member(s) of the study team.

Data safety is monitored by three data safety monitoring board (DSMB) members who are not related to the study.

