5. STUDY VISITS AND PROCEDURES

5.1. Schedule of Visits

A **screening (Visit -1)** session will be conducted. This could take place after a routine clinic visit, or by phone, to perform the Informed Consent (IFC) discussion, review inclusion criteria, collect demographics and basic medical history, and begin MRI safety screening. The Language Battery will also be completed as part of the screening visit. Additionally (in the case of those meeting criteria), patients might visit the Tosa Health Center or Medical College of Wisconsin for stimulation planning. This would entail the use of a Transcranial Magnetic Stimulation (TMS) neuronavigation system. The Language battery and TMS can occur on two separate days prior to the first treatment visit of Treatment Period 1. Subjects will also be invited to **baseline (Visit 1)**. At baseline, the study team will complete fMRI and MEG scans and randomize participants to a treatment group. Procedures within Visit -1 and Visit 1 may be completed in any reasonable order, and may overlap, up to 3 months prior to the first treatment visit of Treatment Period 1. At **Visit 1**, subjects will receive tDCS while simultaneously completing the reading and repetition “trained tasks. Subjects will then return for 9 additional **treatment sessions (Visits 2-10)** where they will receive stimulation or sham, along with trained task administration. At **Visit 10**, subjects will receive MRI, MEG scans, and the Language Battery. These procedures may be completed one month after the last treatment session of Treatment Period 1. At 8-weeks from the last Treatment Period 1 visit, subjects will return for the first **assessment session (Visit 11)**, in which the Language battery, including the trained tasks will be repeated. Subjects will then return 8 weeks later to begin the second series of treatments (**Treatment Period 2, Visits 12-21**) and receive MRI, MEG, and Language Battery on visits 12 and 21. MRI, MEG, and the Language battery will be completed no greater than 3 months prior to the first treatment session of Treatment Period 2, then again no greater than one month after the final treatment session of Treatment Period 2. At each visit during Treatment Period 2, subjects will receive the cross-over treatment (either sham or stimulation) while simultaneously completing the reading and non-word trained tasks. The final

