Study Title: High-Definition Transcranial Direct Current Stimulation (HD-tDCS) in logopenic variant Primary Progressive Aphasia (lvPPA): Effects on Language and Neural Mechanisms.

NCT: NCT03805659

Date of document: July 06, 2023

Statistical Analysis:

- The small sample size in this study precluded group-level statistical analysis.
- Instead focused on a within subject item-level analysis.
- Language performances in each trial period were assessed separately to help control for potential carryover effects and for effects of progressive neurodegeneration.
- The Cochran's Q test was used to determine if there were any differences on a dichotomous variable across the three-trial period timepoints.
- Because the same assessment list/version was used within a given stimulation condition per participant, we coded "right" and "wrong" answers to an individual assessment item as our dichotomous variable.
- If the preliminary Cochran's Q test demonstrated a significant difference ($p<0.05$) between participant responses in a language assessment between two timepoints, a follow-up non-parametric pairwise comparison between the baseline and timepoint list was tested using a McNemar test with a false discovery rate correction (Sheppard et al., 2021; Hung et al., 2017; Tsapkini et al., 2015).
- While the Cochran's Q and post-hoc McNemar test allowed us an objective comparison between timepoints within conditions for each individual participant, we utilized a Wilcoxon-signed rank test to assess participant performance changes between aHD-tDCS and sHD-tDCS (ex: aHD-tDCS T0-T1 percentage change from baseline vs. sHD-tDCS T0-T1 percentage change from baseline). This assessment would allow us a more quantitative direct comparison between treatment conditions on an individual participant (Sheppard et al., 2021). The statistical analyses described were performed using SPSS version 27.0 (IBM, Armonk NY). A p-value of <0.05 was used to describe statistical significance.

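### The SAP's only active-versus-sham test is framed within one participant, where condition is aliased with period and often with item list; its pairs are undefined and no across-participant estimate is specified

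*SAP*

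**What the plan says.** The SAP (Statistical Analysis) gives its reason for working within participants: "The small sample size in this study precluded group-level statistical analysis". Cochran's Q and McNemar tests compare timepoints inside one condition. For active versus sham it says "we utilized a Wilcoxon-signed rank test to assess participant performance changes between aHD-tDCS and sHD-tDCS", with the T0-T1 percentage change in each condition as an example, and adds: "This assessment would allow us a more quantitative direct comparison between treatment conditions on an individual participant". On item lists it says "Because the same assessment list/version was used within a given stimulation condition per participant". Its safeguard against period effects is: "Language performances in each trial period were assessed separately to help control for potential carryover effects and for effects of progressive neurodegeneration". It does not state the unit of pairing, the number of pairs, or whether percentage change is relative or in points.

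The protocol supplies the design facts:
- Section 4.1: "study participants will receive sham during one treatment period and stimulation during the other treatment period". Order is balanced between participants.
- Section 5.4.4: separate item sets or versions by period for picture naming, NAB naming and reading comprehension, phonological short-term memory, rhyme matching and the trained tasks. For the MoCA and NAB oral production the version is tied to condition. No separate lists are stated for digit span, verbal fluency or the Cookie Theft picture.
- Sections 6.2 to 6.4: a composite language score and a group-by-time ANOVA across participants.
- Section 7.8: the pilot is to yield initial estimates of variability and effect size.
- Section 5.1: in Period 2 subjects "receive MRI, MEG, and Language Battery on visits 12 and 21", but "MRI, MEG, and the Language battery will be completed no greater than 3 months prior to the first treatment session of Treatment Period 2".

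**The concern.** The trial asks whether stimulation adds to sham when both are given with the same training. The one SAP test that addresses this sits at a level where the design cannot separate treatment from period. Practice, decline or carried-over training may differ between periods, or one list may be more sensitive to change. Any of these can appear as an active-versus-sham difference for that person. Scores from one person in one period can also move together, which a signed-rank test treating them as independent pairs ignores.

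Two further things are at stake. First, the SAP produces no mean or SD of the active-minus-sham difference, so it does not deliver the pilot's stated output. Second, the change scale matters. Equal gains of 5 points are 5/50 = +10% from a 50% baseline but 5/40 = +12.5% from 40%, so a relative scale can show a difference where the gain in points is the same.

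**Working it through.** **Stated figures.** Neither document gives a sample size, number of pairs or precision for this test, so there is no figure to reproduce. The protocol plans 20 participants in two order groups of ten. The SAP does not give the number analysed.

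**1. Aliasing.** Let D be one participant's active-minus-sham difference in change, τ the stimulation effect, π1 and π2 the changes that belong to each period, and λ the difference between the lists used under active and sham.
- Active first: D = τ + (π1 − π2) + λ + noise.
- Sham first: D = τ − (π1 − π2) + λ + noise.

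One participant supplies one of these lines, so τ cannot be isolated. Measuring change from each period's own baseline removes a difference in level between periods, but not π1 − π2, which is a difference in change. Averaging the two order means cancels π1 − π2. If the list follows period, its effect is part of π and cancels too. If it follows condition, λ stays. Carryover that differs by order also stays.

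**2. Can the test reach p<0.05?** With k untied pairs the smallest exact two-sided p is 2/2^k: k = 2 gives 0.50, k = 5 gives 0.0625, k = 6 gives 0.031 and k = 7 gives 0.016. If the pairs are the two follow-up changes (T0-T1 and T0-T2), significance is impossible.

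**3. If the pairs are test scores.** Assume k = 7, the number of scores in the protocol's composite (section 6.3); the SAP does not say this. With independent pairs and no shift, p<0.05 requires a rank sum of 0, 1 or 2 in either tail: 2 × 3/2^7 = 4.7%. The other rates come from 200,000 simulated sets of normal differences with common correlation ρ, or with a mean shift and ρ = 0, and no stimulation effect:

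| Pairs | None | ρ=0.1 | ρ=0.3 | ρ=0.5 | Shift 0.25 SD | Shift 0.5 SD |
|---|---|---|---|---|---|---|
| 6 | 3.1% | 6.5% | 16% | 28% | 5.1% | 11% |
| 7 | 4.7% | 11% | 25% | 40% | 8% | 19% |
| 8 | 3.9% | 10.5% | 26% | 42% | 7.4% | 19% |

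Correlations and shifts are assumptions; the documents give none.

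**4. Period 2 baseline.** Three months is about 13 weeks, so the earliest permitted date is about 16 − 13 = 3 weeks after Period 1 ends.

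**5. Precision of an across-participant estimate.** For a and b participants in the two orders (n = a + b), the 95% half-width in within-order SDs is t(0.975, n−2) × 0.5 × √(1/a + 1/b).
- 2+2: 4.303 × 0.5 × 1 = 2.15.
- 3+3: 2.776 × 0.5 × 0.816 = 1.13.

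A plain mean of D would leave (a−b)/(a+b) of π1 − π2 in the estimate: (3−1)/4 = one half at 3+1, none at 2+2.

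**The case against.** The SAP is open about the small sample, the study is a pilot, and analysing each period from its own baseline is a real partial safeguard. The Wilcoxon sentence speaks of participant performance changes, so it could mean pairing across participants. That reading conflicts with the SAP's own description of the comparison and with its exclusion of group-level analysis. If it is what was done, the SAP needs to say so.

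Several stronger readings are tempting, and the documents do not support them.
- That the pairs must be test scores. Follow-up changes are equally possible, and they could never give a significant result. The inflated rates hold only on the test-score reading.
- That no across-participant comparison was ever planned. The protocol has one; the gap is in the SAP. Restoring that ANOVA is not straightforward, because its group factor means the two order groups in section 6.2 but sham versus stimulation in section 6.4.
- That every list follows period, so balanced order removes list effects. For the MoCA and NAB oral production the version follows condition.
- That the SAP attributes within-condition change to stimulation. It presents Cochran's Q and McNemar only as comparisons of timepoints, so their error rates are not evidence for this point.
- That the Period 2 baseline was taken early. The window allows it; nothing shows that it happened, and the treatment washout stays at 16 weeks.

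**Conclusion.** The point stands and should be fixed before any participant's active-versus-sham p-value is interpreted. The aliasing of condition with period follows from the design and needs no assumption. Aliasing with list applies to most of the battery, but not to tests without separate lists. The undefined pairs decide whether the test is powerless (smallest p 0.50 with two pairs) or prone to false positives. With seven assumed test scores, rejection with no stimulation effect is about 11% to 40% over assumed correlations of 0.1 to 0.5, or 8% to 19% for assumed shifts of 0.25 to 0.5 SD alone, against 4.7%. These rates show the possible size; they do not estimate what occurred in this trial. The missing mean and SD of the active-minus-sham difference is a separate shortfall against protocol section 7.8.

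**What to change.** - State which observations the Wilcoxon test pairs and how many, and whether change is relative or in percentage points.
- Label any within-participant Wilcoxon result, and the Cochran's Q and McNemar results, as descriptive, and do not attribute them to stimulation.
- For each assessment, tabulate every participant's active-minus-sham difference in change with treatment order and list or version. Report trained and untrained items separately, since section 5.4.4 has only half of those items practised.
- With four or more participants and both orders represented, report the average of the two order means with the pooled within-order SD and a 95% CI on n−2 degrees of freedom, without a significance test. Otherwise list the individual differences and state that period cannot be separated from treatment.
- Where version is tied to condition, state that the list effect remains in the estimate.
- Report each participant's interval from the end of Period 1 to the Period 2 baseline, and name carryover and decline as remaining limitations.

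The cost is SAP wording and a re-analysis of data already collected. The SAP is written in the past tense, so the new estimate is post hoc and should be labelled so. Intervals will be wide (half-width 2.15 within-order SDs at 2+2, 1.13 at 3+3), and there will be fewer nominally significant p-values.

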Efficacy Assessments	(i) Consent rate and treatment completion rate (ii) Statistically significant differences between baseline and post- tDCS stimulation performance on a series of language metrics.
Unique Aspects of this Study	This is the first study to evaluate the efficacy of HD-tDCS for the treatment of language deficits of lvPPA, a neurodegenerative and progressive condition with no known effective treatment. It would also be the first study to access whether HD-tDCS can increase brain functional connectivity and regulate abnormal patterns of neuronal frequencies and synchronizations in this patient population.

Table of Contents

1. Study Objectives	5
2. Background and Significance	6
3. Rationale	7
4. Study Design	8
5. Study Visits and Procedures	9
6. Data Management	15
7. Data Safety Monitoring Plan	16
8. References	21

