1.3. Outcome Measurements

The following outcome measurements will be used to test our proposed hypothesis:

- **Primary outcome measures:** Language performance as assessed at baseline and post-stimulation procedure (time frame: 2 weeks)
- **Secondary outcome measures:** Language network resting state changes after stimulation procedure (time frame: 2 weeks)
- **Tertiary outcome measures:** Resting-state neuronal frequencies and synchronizations changes after stimulation procedure (time frame: 2 weeks)

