6. DATA MANAGEMENT

6.1. A secure web-based system will be used to enroll patients and obtain the randomly assigned treatment group. Data forms will be printed, completed, and entered into the database using a secure web-based application. The database will be monitored for completeness, consistency, accuracy, and timeliness. No patient-identifying information will be stored in the database. To ensure that data are secure from external violation, computer systems containing study data will be password protected, and physical access to the computer systems will be limited.

6.2. Determination of changes in Language Function and Concurrent Improvement in Network Activity.

The language and MRI/rfMRI datasets will be obtained at baseline (before sham/active tDCS administration) and on the last day of each 2-week treatment period. These two time points will be denoted $t = 1, 2$. The two 10-

subject groups, both of which will receive both sham and active tDCS at different treatment phase, will be denoted $g = 1, 2$. The set of Language (LG) scores for subject s , from group g , at time t will be denoted $LG(s, g, t)$, where $s = 1, \dots, 10$; $g = 1, 2$; and $t = 1, 2$. The Language-Network functional connectivity (LFC) calculated between the left posterior temporal and inferior parietal cortex for subject s , from group g , at time t will be denoted $LFC(s, g, t)$.

6.3. Language Changes Due to Stimulation. Scores across all tests within the language battery will be combined into one composite measure to facilitate assessment of overall language performance across domains. All seven scores will be normalized to a Z-score by transforming individual raw test scores according to the mean and standard deviation of the scores for all subjects. Then, Z-scores of each test will be averaged to obtain an individual composite language Z-score (McConahey et al., 2017). We will employ age, years of education, gender, and gray matter (GM) volume as time-invariant covariates to obtain residual variables to determine the LG changes due to stimulation. We will model the LG score as a function of these nuisance regressors. This regression will be performed using all the data (i.e., all subjects, all groups, and all times):

$$\Delta LG(s, g, t) = \beta_0 + \beta_1 Age(s) + \beta_2 Edu(s) + \beta_3 GM(s) + \beta_4 Gender(s) + Res(s, g, t)$$

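### The SAP's only active-versus-sham test has no multiplicity control, no stated pairing unit or number of tests, and no deciding follow-up, so any single p<0.05 can be reported as a stimulation effect

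*SAP*

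**What the plan says.** The SAP (Statistical Analysis) rules out group-level testing because the sample is small, and works within participants in two layers.

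- **Within a condition.** Cochran's Q asks "if there were any differences on a dichotomous variable across the three-trial period timepoints". Where Q is significant, "a follow-up non-parametric pairwise comparison between the baseline and timepoint list was tested using a McNemar test with a false discovery rate correction".
- **Between conditions.** "we utilized a Wilcoxon-signed rank test to assess participant performance changes between aHD-tDCS and sHD-tDCS". The input is percentage change from baseline, and T0-T1 appears only as an example. No screening test, correction, pairing unit or number of tests is given.

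The closing rule covers everything: "A p-value of <0.05 was used to describe statistical significance".

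Protocol 1.3 defines the primary outcome as "Language performance as assessed at baseline and post-stimulation procedure (time frame: 2 weeks", and the Protocol Summary (Endpoints) repeats that time frame. Protocol 6.3 adds: "Scores across all tests within the language battery will be combined into one composite measure". The Protocol Summary (Efficacy Assessments) speaks more loosely of "performance on a series of language metrics". The SAP mentions neither the two-week limit nor the composite.

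**The concern.** In a sham-controlled crossover, efficacy rests on active versus sham. Change within one condition can come from practice on repeated items, from the language training given in both conditions, or from disease progression. The SAP therefore corrects the tests that cannot by themselves show a stimulation effect. It leaves the one test that can show it at an unadjusted 0.05, however many times it is run.

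Nothing in the SAP tells a reader which Wilcoxon result decides. Correcting the Cochran's Q and McNemar results more thoroughly would not change this, because the Wilcoxon p-values form a separate family. The protocol intends these pilot data to inform a later pivotal trial, so a chance result could carry into its planning.

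**Working it through.** The documents give no error rate for the set of Wilcoxon tests, so there is no planned figure to reproduce. The check is how the risk varies with what the SAP leaves open.

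**Inputs**
- Level per test: 0.05 (SAP). Two-sided is assumed.
- Follow-ups: three timepoints less baseline = 2 (SAP). I take T1 as the battery at the end of the treatment period and T2 as the 8-week visit (Protocol 5.1). The SAP does not define the labels.
- Assessments: 7 (the number of scores in Protocol 6.3) to 9 (my count of the tests in Protocol 5.4.4: naming, fluency, digit span, phonological short-term memory, rhyme matching, speech sample, reading comprehension, MoCA, trained tasks). The documents do not state 9.
- Participants analysed: not given. Four is assumed for illustration.

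**Formulas**
- At least one false positive in k independent tests: 1 − 0.95^k.
- Correlated tests: simulation of k equally correlated normal statistics, 200,000 draws.
- Smallest exact two-sided signed-rank p with n pairs, no ties or zeros: 2 × 0.5^n.

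**Reading A: assessments within a participant are the pairs.** There is one test per follow-up, so k = 2.
- Per participant: 1 − 0.95^2 = 0.0975.
- Four participants, 8 tests: 1 − 0.95^8 = 0.34.
- With 7 pairs the smallest exact p is 2 × 0.5^7 = 0.016, so 0.05 can be reached. The exact test's true level is slightly under 0.05 (0.047 at 7 pairs, 0.039 at 9), so these risks are slight overestimates.

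**Reading B: one test per assessment and follow-up within a participant.** k = 7 × 2 = 14 to 9 × 2 = 18.

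| Correlation | k = 14 | k = 18 |
|---|---|---|
| 0 | 1 − 0.95^14 = 0.51 | 1 − 0.95^18 = 0.60 |
| 0.5 | 0.35 | 0.40 |
| 0.8 | 0.20 | 0.22 |

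**Reading C: participants are the pairs.** The same 14 to 18 tests now cover the whole trial.
- n = 4: 2 × 0.5^4 = 0.125. n = 5: 0.0625. n = 6: 0.031.
- With five or fewer participants no exact test can reach 0.05. The normal approximation gives a minimum of 0.068 at n = 4 and 0.043 at n = 5. The SAP does not say which form was used.

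**With a correction.** Under B, a simulated Benjamini-Hochberg correction over 14 or 18 independent tests with no true effect gives at least one rejection with probability 0.050 or 0.051. Under A, restricting to T0-T1 leaves one test per participant. Four uncorrected tests give 1 − 0.95^4 = 0.19, and correcting across the four independent tests brings this back to 0.05.

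**The case against.** Three stronger readings are tempting, and the documents do not support them.

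**That 14 to 18 uncorrected tests were run on each participant.** This is reading B, and it is an inference. Percentage change belongs to an assessment score; a single item scored right or wrong has no useful percentage change. Item sets also differ between the two periods (Protocol 5.4.4, for example 80 pictures for each), so items are not naturally paired across conditions. The count of 9 includes measures that fit right/wrong scoring poorly, such as the speech sample and vocal reaction times. Reading A sits better with the SAP's description of a comparison for one participant.

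**That no text settles the follow-up or the measure.** The protocol gives the two-week time frame twice and names a composite. Its looser reference to several metrics does not contradict a composite built from them. The gap is that the SAP does not carry these forward.

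**That the risk is always several times 0.05.** Per participant under A it is less than twice 0.05. Under C with four participants and exact tests it is zero.

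It is also fair to say that this is a pilot meant to estimate variability and effect sizes, and that the SAP makes no confirmatory claim. That lowers the weight of the point. It does not remove it: the SAP sets a significance threshold and already accepts multiplicity control for the McNemar tests.

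**Conclusion.** The point holds. The active-versus-sham comparison is outside the stated correction, its pairing and number of tests are undefined, and the SAP names no deciding assessment or follow-up although the protocol offers a two-week time frame and a composite.

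The size cannot be fixed from the documents. Per participant it runs from 0.0975 (reading A, independent tests) to between 0.20 and 0.60 (reading B, correlation 0.8 to 0). Under reading C it depends on the number analysed. The assumptions are valid two-sided tests at 0.05, two follow-ups and 7 to 9 assessments; the figures across participants also assume four independent participants. The undefined pairing is the first thing to settle, because the other numbers follow from it. I rate this a cheap improvement.

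**What to change.** In the SAP and the report:

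1. State what forms the Wilcoxon pairs (items, assessments or participants) and how many tests were run.
2. Name T0-T1, the end of the two-week period, as the deciding active-versus-sham follow-up, in line with Protocol 1.3. Label T0-T2 exploratory.
3. Apply the false discovery correction already used for McNemar to all T0-T1 Wilcoxon p-values as one family, across assessments, participants or both, whichever are tested separately.
4. Report adjusted and unadjusted p-values together, and claim no stimulation effect from an unadjusted p-value alone.

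The SAP is written in the past tense, so the analyses appear to be done. The cost is a few sentences and one adjustment of existing p-values, with no new data. The small downside is that some nominally significant results may lose significance.
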